15.3. Definitions of Units of Analysis

The definitions of TP, TN, FP, and FN at the units of analysis of orientation, patient and primary specimen are provided in Table 15.1.

SBI-CIP 20-002 Rev: v1.8 A prospective multi-center clinical study evaluating the use of PD G 506 A and the Eagle V1.2 Imaging System for the visualization of carcinoma during breast conserving surgery	Page: 97 of 157
---	-----------------

Table 15.1: Levels of Analysis and Diagnostic Performance Definitions

Diagnostic Performance	Orientation Level	Patient Level	Primary Specimen Level
Parameter	Analysis	Analysis	
_			Analysis A primary specimen level analysis evaluates each biopsy from the bisected primary specimen (i.e., primary tumor mass) as a single data point. At most, there will be one FL-positive and one FL-negative biopsy per patient included in the analysis.
	An orientation is comprised of two contiguous tissue surfaces that have been separated by a scalpel (or other surgical tool e.g., electrocautery) during tissue resection. The tissue surfaces are from the primary specimen, cavity shave specimens, and the final cavity surface. An orientation is described based on the anatomical location of the contiguous tissues (e.g. S, M, P, L, I, A).		
True Positive	Orientation that is fluorescence positive and histopathology positive.	Patient has at least one TP orientation without any FN orientations	Fluorescence is observed in the primary specimen biopsy that is histopathology-positive for carcinoma
True Negative	FL-negative orientation with final margin for that orientation from cavity shave specimens or primary specimen (if no shaves taken) negative on histopathology	Patient has all TN orientations	No fluorescence is observed in the primary specimen biopsy that is histopathology-negative for carcinoma

SBI-CIP 20-002	Rev: v1.8	A prospective multi-center clinical study evaluating the use of PD G 506 A and the Eagle V1.2 Imaging System for the visualization of carcinoma during breast conserving surgery	Page: 98 of 157
-----------------------	--------------	--	-----------------

Diagnostic Performance Parameter	Orientation Level Analysis	Patient Level Analysis	Primary Specimen Level Analysis
False Positive	FL-positive orientation with final margin for that orientation from cavity shave specimens or primary specimen (if no shaves taken) negative on histopathology	Patient has at least one FP orientation without any FN or TP orientations	Fluorescence is observed in the primary specimen biopsy that is histopathology-negative for carcinoma
False Negative	FL-negative orientation with final margin for that orientation from cavity shave specimens or primary specimen (if no shaves taken) positive on histopathology	Patient has at least one FN orientation has at least	No fluorescence is observed in the primary specimen biopsy and the biopsy is histopathology- positive for carcinoma

SBI-CIP Rev 20-002 v1.8	A prospective multi-center clinical study evaluating the use of PD G 506 A and the Eagle V1.2 Imaging System for the visualization of carcinoma during breast conserving surgery	Page: 99 of 157
----------------------------	--	-----------------

15.4. Analysis Populations

The analysis populations and timepoints are described below.

15.4.1. mITT Analysis Population

The mITT population includes all subjects who are randomized (Arm 1 and Arm 2), dosed (Arm 2 only), have the fluorescence imaging performed (Arm 2 only) and have recorded surgical pathology data. The mITT will be used for all *patient-level* and *orientation-level* analyses. Missing data will be imputed, and full detail will be provided in the Statistical Analysis Plan.

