following index BCS (Arm 1 and Arm 2).	suspected residual disease (patient-level analysis; Arm 1 and Arm 2).	# of patients in Arm 1 that underwent a 2 nd surgery on the ipsilateral breast within 1 year of index BCS # of patients in Arm 1 # of patients in Arm 2 that underwent a 2 nd surgery on the ipsilateral breast within 1 year of index BCS # of patients in Arm 2	x100%	
16. To characterize the impact of FGR on the rate of 2 nd surgery shortly after index BCS (Arm 1 and Arm 2).	Percentage of patients receiving an early 2 nd surgery (planned or actual) on the ipsilateral breast related to positive final margins prior to radiation or medical management (patient-level analysis; Arm 1 and Arm 2).	# of patients in Arm 1 that underwent or are scheduled to undergo a 2 nd surgery on the ipsilateral breast due to positive SoC final margins following initial BCS prior to radiation or medical management # of patients in Arm 1	x100%	Patient-level early reoperation rate.
		P(2.16b) Arm 2 only = # of patients in Arm 2 that underwent or are scheduled to undergo a 2 nd surgery on the ipsilateral breast due to positive FGR final margins following initial BCS prior to radiation or medical management # of patients in Arm 2	x100%	

SBI-CIP 20-002 Rev: v1.8 A prospective multi-center clinical study evaluating the use of PD G 506 A and the Eagle V1.2 Imaging System for the visualization of carcinoma during breast conserving surgery Page: 38 of 157	·
--	---

Secondary Objectives	Parameter Description	Parameter Formula	Abbreviated Description
17. To characterize the impact	Sum of the weight (mg) of all tissue	P(2.17a) =	Amount of tissue removed
of FGR during BCS on the	removed based on SoC compared to the	Mean SoC tissue weight (mg) Arm 1 and Arm	with FGR beyond SoC.
amount of tissue removed	sum of the weight (mg) of all tissue	2:	
(Arm 1 and Arm 2).	removed based on FGR (patient-level	SoC tissue weight = Primary specimen (mg) +	
	analysis; Arm 1 and Arm 2).	SoC-driven cavity shave specimen(s) (mg)	
		P(2.17b) =	
		Mean FGR tissue weight (mg) Arm 2 only:	
		Total tissue weight = FL-driven cavity shave	
		specimen(s) (mg)	
18.To characterize the impact	Patient satisfaction with the cosmetic	P(2.18a) =	Patient satisfaction.
of FGR during BCS on the	outcome of breast conserving surgery	Mean Breast-Q Breast Conserving Therapy	
patient-reported cosmetic	performed based on SoC in	Module satisfaction with breasts score before	

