Only data from participants in Part B will be used for the analyses of primary and secondary efficacy. Data from all participants in both Part A and Part B will be used for the evaluation of safety.

In Part B of the study, participants will be randomized in a ratio of 1:6 (Arm 1 [SoC]: Arm 2 [PD G 506 A]).

The randomization will be stratified by breast cancer type (invasive carcinoma with or without in situ carcinoma vs. in situ carcinoma alone). This will ensure an approximate ratio of 1:6 within each type of breast cancer. Preoperative diagnosis based on diagnostic tissue sampling performed during screening (e.g. percutaneous core needle biopsy, fine-needle aspiration cytology) will be

SBI-CIP 20-002 Rev: v1.8 A prospective multi-center clinical study evaluating the use of PD G 506 A and the Eagle V1.2 Imaging System for the visualization of carcinoma during breast conserving surgery	Page: 46 of 157
---	-----------------

used for stratification. Permuted blocks will be used to construct the randomization schedule and the randomization will be implemented using an interactive web response system.

Data from the SoC arm (Arm 1) will not be used for statistical analysis of the primary and most secondary endpoints. The purpose of the SoC arm is to compare resected tissue weight, patient reported cosmetic outcomes, re-excision prior to initiation of adjuvant therapies, re-excision within 1-year of index BCS, and safety between study arms as well as to minimize bias introduced into the SoC procedure if the *surgeon* is aware that they have an opportunity to revise the margins further after SoC is complete. A 3-month, 6-month and 1-year follow-up will be performed to evaluate patient reported cosmetic outcomes as well as the rate of re-excision across both study arms. The 6-month and 1-year follow-up data will be collected as an extension phase to the study, meaning database lock and analysis of all other endpoints will be performed following the last patient's 3-month follow-up data is collected. Analysis of 6-month and 1-year data will occur after the last patients 1-year visit. The clinical study report will be appended to include the 6-month and 1-year data, when available.

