Using a randomization ratio of 1:6 (Arm 1-SoC; Arm 2: PD G 506 A), a total sample size of 525 patients (Arm 1: N=72; Arm 2: N=428) would be required, accounting for a 5% loss to follow-up. The primary efficacy analysis will be based on the mITT (modified intention-to-treat population), which includes all Part B patients randomized to Arm 2 who undergo surgery and have recorded surgical histopathology data.

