15.7. Secondary and Exploratory Endpoint Analysis

Secondary and exploratory endpoints based on *patient-level* data will be analyzed using similar methods to the primary and key secondary endpoints, using Wilson (score) confidence intervals. Re-operation rates will be compared between treatments using Fisher's exact tests.

Secondary and exploratory endpoints based on *orientation-level, primary specimen-level, and point-level* data will be analyzed using a weighted estimator, proposed by Lee and Dubin (Lee and Dubin, 1994), which takes into account the correlation (clustering) of the margins within a patient. This method will be used to calculate the estimates and two-sided 95% confidence intervals.

Descriptive statistics will be used to summarize the weight of resected tissue specimens (SoC specimens vs. FGR specimens). Mean total tissue weight (Arm 1 vs. Arm 2) will be compared using a two-sample t-test.

Breast-Q survey results will be summarized using actual values and change from baseline values using descriptive statistics. The difference in change scores between Arm 1 and Arm 2 will be summarized descriptively and presented along with a 95% confidence interval on the difference in means. For the Breast-Q survey results at 3 months, if the lower bound of this confidence interval is \geq - 10 then non-inferiority will be claimed. Results at 6 months and 1 year will be described with summary statistics. For the analysis of Breast-Q survey results, the previously defined minimal important difference as the reference point for what patients consider a meaningful change in Breast-Q scores. The minimal important difference is defined as: "The smallest difference in score in a domain of interest that patients perceive as beneficial and which would mandate, in the

|--|

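### The mITT requires dosing and imaging in Arm 2 only, yet it is assigned to the randomised comparisons of re-operation, tissue weight and Breast-Q

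*Combined protocol and SAP*

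**What the plan says.** Section 15.4.1 admits randomised patients to the mITT if they are "dosed (Arm 2 only), have the fluorescence imaging performed (Arm 2 only) and have recorded surgical pathology data". Dosing and imaging are conditions for Arm 2 only; recorded pathology is a condition for both arms. On scope, the section says: "The mITT will be used for all *patient-level* and *orientation-level* analyses".

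Section 8.1 gives Arm 1 a comparative job: "The purpose of the SoC arm is to compare resected tissue weight, patient reported cosmetic outcomes", followed by re-excision and safety. Section 7.2.2 labels P(2.15)–P(2.18) as patient-level endpoints in both arms; the re-operation endpoint, for example, reads "suspected residual disease (patient-level analysis; Arm 1 and Arm 2". Section 15.7 then sets out the comparisons: "Re-operation rates will be compared between treatments using Fisher's exact tests"; "Mean total tissue weight (Arm 1 vs. Arm 2) will be compared" by a two-sample t-test; and Breast-Q at 3 months is judged for non-inferiority against a margin of -10. Section 15.7 names no separate population for any of these.

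Section 15.2 and the Synopsis (Appendix 1) describe a different mITT, "which includes all Part B patients randomized to Arm 2 who undergo surgery and have recorded surgical histopathology data". That version has no dosing or imaging condition, and it has no Arm 1.

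**The concern.** Missing a dose or missing imaging happens after randomisation. Removing patients for it in one arm only means the two groups compared are no longer the groups that were randomised. For single-arm and diagnostic endpoints the imaging condition is natural, because an un-imaged patient has no fluorescence result to score. For re-operation, tissue weight and Breast-Q it is not needed: these outcomes exist whether or not the patient was imaged.

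At stake are the comparisons for which Arm 1 was included, one of which supports a non-inferiority claim on cosmetic outcome. Imputation, which 15.4.1 promises for missing data, does not bring back patients who are outside the population.

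**Working it through.** **1. The plan's own figure, and whether it depends on this.** Section 15.2 uses a null of 1%, an alternative of 3%, two-sided 0.05 and 90% power.

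n = [(1.96·√(0.01·0.99) + 1.2816·√(0.03·0.97)) / 0.02]² = 427.7, so 428 in Arm 2.

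428 × 7/6 = 499.3, about 500 in total; 500 × 1.05 = 525. The figures reproduce. They rest on the single-arm endpoint P(1.1) alone and are untouched by this point.

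**2. Which population governs P(2.15)–P(2.18).**

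- 15.4.1: the imaged mITT, by its statement of scope.
- 15.2 and Synopsis: an mITT with no Arm 1, which cannot serve a between-arm comparison.
- 7.2.2: the denominators of P(2.15) and P(2.16) are simply the number of patients in each arm. P(1.1), P(2.10b), P(2.11b) and P(2.12b) instead name imaged Arm 2 patients.
- 15.4.2 and 15.4.3: the only other sets are safety and primary specimen biopsy.

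These statements do not agree, and no as-randomised set is defined.

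**3. Who is dropped.** Under 12.4.3 the surgeon's assistant images excised specimens in both arms before the envelope is opened. Cavity imaging follows unblinding, in Arm 2 only. Section 15.4.1 does not say which imaging counts; if it is cavity imaging, the criterion is settled after unblinding. The clear case is an Arm 2 patient who has surgery but is not dosed or not imaged, for example through device failure, and who is not terminated. Such a patient leaves the mITT. An Arm 1 patient who did not take placebo but has pathology stays in.

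**4. Illustration for re-operation.** Assumptions, none of them from the plan except the base rate: no true effect; p = 23.6% in both arms (average US re-excision rate, 6.1.1); a share e of Arm 2 excluded, 2–10% (about 9 to 43 of 428); excluded patients at r = 1.5–2 times the average rate.

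Rate in the remaining Arm 2 patients = (p − e·r·p)/(1 − e).

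| e | r | Arm 2 mITT | Shift (points) | Two-sided type I error |
|---|---|---|---|---|
| 2% | 1.5 | 23.4% | −0.2 | 0.050 |
| 2% | 2.0 | 23.1% | −0.5 | 0.051 |
| 5% | 1.5 | 23.0% | −0.6 | 0.052 |
| 5% | 2.0 | 22.4% | −1.2 | 0.056 |
| 10% | 1.5 | 22.3% | −1.3 | 0.057 |
| 10% | 2.0 | 21.0% | −2.6 | 0.077 |

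Type I error uses a normal approximation with 72 patients in Arm 1 and 428·(1 − e) in Arm 2. The shift is 0.04 to 0.48 standard errors.

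**5. Direction for the other outcomes.** Un-imaged Arm 2 patients have no fluorescence-driven shaves.

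- *Tissue weight.* If imaged patients lose on average w of extra tissue, the as-randomised mean is (1 − e)·w while the mITT reports w. Other things equal, the mITT raises the Arm 2 figure by 2–10% of w.
- *Breast-Q.* If excluded patients score d points worse, the mITT flatters Arm 2 by e·d. For d = 5 to 20 this is 0.1 to 2.0 points, against a margin of 10. If instead they score better because less tissue was taken, the sign reverses. Including patients who had no fluorescence-guided resection also pulls the difference toward zero, which makes non-inferiority easier to show.

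**The case against.** The strongest reply is that little of this is left once the rest of the plan is read.

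- **Terminated patients.** A surgeon stopping study procedures during the operation is the plan's example of early termination (12.10). Section 11.1 ends non-safety data collection on termination and replaces anyone terminated before Week 2 is complete. Neither rule is limited to one arm. This stands: those patients lack outcome data whichever population is named, so the asymmetry in 15.4.1 acts on non-terminated patients who missed dosing or imaging.
- **Denominators.** P(2.15) and P(2.16) can be read as all patients by arm, and 15.5 points to Section 7 for the formulas. This stands as an ambiguity, not a cure, because 15.4.1 expressly assigns the mITT.
- **Deferral.** Section 15.1 leaves further analysis detail to the SAP, and the Amendment 8 summary says the mITT was adjusted on FDA advice. Neither says that the imaged set suits the between-arm comparisons.

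A reader might also infer that hard or unstable operations are the ones left un-imaged, so that the exclusion favours Arm 2. Nothing in the documents says so, and step 5 shows the sign can reverse for tissue weight and Breast-Q. Nor is Arm 1 unselected: it too must have recorded pathology. The 5% in 15.2 is an allowance for loss to follow-up and should not be taken as a rate of missed imaging.

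**Conclusion.** The point holds as a defect in how the population is specified. Followed literally, the plan applies a post-randomisation exclusion to one arm of comparisons that Arm 1 was included to provide, and its own statements of the mITT and the denominators conflict.

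It does not follow that these comparisons are seriously biased, or biased toward Arm 2. The direction and size cannot be derived from the documents. Under the assumed inputs (2–10% excluded, 1.5–2 times the risk, 23.6% base rate) the effect on re-operation is about 0.2–2.6 points and type I error about 0.050–0.077, small unless exclusions approach 10% at double risk.

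P(1.1) and P(2.1)–P(2.3) use Arm 2 only and are not touched by this comparison problem. The change should be made, but the trial's primary conclusion does not hang on it.

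**What to change.** 1. Keep the imaged mITT for the single-arm and diagnostic endpoints, and state which imaging satisfies the criterion.
2. Analyse re-operation and tissue weight, P(2.15)–P(2.17), in all Part B patients as randomised who underwent index surgery, in both arms, regardless of dosing or imaging. The surgery condition is the same in both arms, and the surgeon is blinded until standard-of-care resection is complete.
3. For Breast-Q non-inferiority, P(2.18), report both the as-randomised and the imaged populations and require consistent conclusions before claiming non-inferiority.
4. State this in 15.4.1 and 15.7, and reconcile the definitions in 15.2 and the Synopsis and the denominators in 7.2.2.
5. Clarify in 11.1 and 12.10 that un-imaged patients who have not withdrawn consent stay in Breast-Q and re-operation follow-up. This should be settled early, because Breast-Q data not collected on time cannot be recovered.

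The cost is protocol and SAP wording, a small amount of extra follow-up data and slight dilution of the Arm 2 contrast. The sample size, primary endpoint and key secondary endpoints stay as they are.

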15.4.2. Safety Population

The safety population includes all subjects who are randomized (Arm 1 and Arm 2) and receive PD G 506 A (Arm 2 only); this population will be used for all safety analyses.

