10.1.2.5. Preparation and Administration of the Placebo

Participant's randomized to Arm 1 will receive drinking water as the placebo. Calculate the administration volume, in mL, according to the following:

Administration Volume (mL) =
$$\frac{Patient\ Weight\ (kg) \times 20\ ml}{30\ kg}$$

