12.3. Enrolment and Randomization (no visit, Days -30 to Day 0)

Consented patients meeting all eligibility criteria at the time that their surgery is scheduled will be enrolled in the study. Sites must submit the Enrolment Form to the study sponsor for review and approval a minimum of 2 business prior to the patient's scheduled surgery. Enrolment and randomization will take place with sufficient time prior to the scheduled surgery to allow for the investigational drug prescription to be filled. Participants will be notified verbally (in person or via telephone) that they have been enrolled in the study. Consented patients that do not meet the eligibility criteria at the time their surgery is scheduled will not be enrolled in the study and will be notified of such verbally (in person or via telephone).

Study patients scheduled to undergo a bilateral lumpectomy procedure will only have the study procedure performed on one breast. The breast to be included in the study will be identified and documented by the surgeon at the time of enrolment.

Following enrolment, the *surgeon* will complete the investigational drug prescription order and submit it to the 3rd party responsible for dispensing the investigational drug (e.g. pharmacist). The prescription order will specify the dose, date and time of pick-up. The 3rd party responsible for dispensing the investigational drug will use the IVRS/IWRS system to identify to which study arm a participant has been randomized.

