12.10. Early Termination Visit

If early termination occurs prior to administration of the investigational drug (and use of the Eagle V1.2 Imaging System) no additional study specific procedures or evaluations are required and no early termination visit is required. If early termination occurs following administration of the investigational drug (e.g. during the surgery the *surgeon* decides it is not in the best interest of the patient to proceed with the study specific data collection), safety data including AEs and medical device problems will be collected and recorded on the procedure day (Day 1). The participant will continue to be followed for AEs until the Week 2 Visit. No specific early termination visit is required.

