15.8. Safety Analysis

The safety of the procedure and device will be assessed for both Arm 1 and Arm 2. The rates of procedure-related WHO grade 3-5 adverse events, drug-related WHO grade 3-5 adverse events, and device-related WHO grade 3-5 adverse events will be summarized descriptively by treatment arm. Additional summaries may be performed. Full details will be provided in the SAP.

16. Data Management

Data management will be performed according to the Data Management Plan to ensure the accuracy, quality and integrity of the data.

eCRFs will be used to capture study assessments and data. The study coordinator or other delegated study staff will enter data from source documents into the eCRFs. Training will be provided for the electronic data capture (EDC) system. All study staff using the EDC system must have the necessary education, training, and experience or any combination of these. The investigator will be responsible for documenting employee education, training, and previous experience that pertain to the EDC system for all site staff using the EDC system. The investigator must maintain adequate security of the EDC system, including documentation that all users have been trained and a list of authorized users. To ensure all data entries can be tracked, all personnel responsible for data entry

|--|

must obtain a unique user identification (user ID) and password before any data can be entered in the eCRFs. Authorized study staff will be assigned a unique user ID only after receiving training.

The investigator must make study data accessible to the site monitor, other authorized representatives of the sponsor, and the appropriate regulatory authority inspectors. The eCRF for each subject will be checked against source documents at the site by the site monitor, and a final copy of the eCRF will be signed by the investigator with an electronic signature. A copy of the final eCRFs will be provided to the investigator in PDF after study closure to be kept in the investigator's study files. See the Data Management Plan for additional details.

17. Deviation from the Clinical Investigation Plan

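### The safety population requires dosing in Arm 2 but only randomisation in Arm 1, and its wording leaves out Part A; it should be defined by study product received

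*Combined protocol and SAP*

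**What the plan says.** Section 15.4.2 defines the set: "The safety population includes all subjects who are randomized (Arm 1 and Arm 2) and receive PD G 506 A (Arm 2 only"). It adds that "this population will be used for all safety analyses". The receipt condition is tied to one arm, yet the other arm also has a product to receive. Section 10.1.2.5: "Participant's randomized to Arm 1 will receive drinking water as the placebo".

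Section 15.8 uses the set for a description by arm: "The safety of the procedure and device will be assessed for both Arm 1 and Arm 2", and related events of grade 3 to 5 are tabulated in the same way ("device-related WHO grade 3-5 adverse events will be summarized descriptively by treatment arm"). Section 8.1 lists safety among the comparisons for which the SoC arm exists.

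Patients can be randomised and never treated. The heading of Section 12.3 gives a window ("Enrolment and Randomization (no visit, Days -30 to Day 0"). Section 11 provides for withdrawal if surgery moves away from a study site or eligibility is lost. Section 10.8 ends participation if a listed phototoxic drug is started before dosing. Section 12.10 has a rule for this group, opening "If early termination occurs prior to administration of the investigational drug", and asks for nothing further from them. Section 11.1 replaces anyone who leaves before completing the Week 2 visit, but does not say that the replaced patient leaves the safety set.

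Sections 8.1 and 15.2 bring all Part A patients into the safety evaluation. Part A is not randomised.

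**The concern.** A safety denominator should contain people who were exposed to what is being compared. Here one arm is filtered on exposure and the other is not. A patient lost between randomisation and dosing has had no study product, no study imaging and no study surgery, so she adds to the Arm 1 denominator and cannot add to its numerator of related events. Her counterpart in Arm 2 disappears from both. Arm 1 then shows a lower related-event rate than its treated patients had, with no drug effect behind the difference.

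The mITT definition in Section 15.4.1 also ties dosing to Arm 2, but it requires surgical pathology results without limiting that to one arm, which removes patients who never had surgery. The safety definition has no such filter.

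Two further gaps sit in the same sentence. It gives no rule for a patient who receives the other arm's product. And, taken literally, it has no place for Part A.

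**Working it through.** **Arm sizes (the plan's own figures).** Section 15.2: null 1%, expected 3%, two-sided 0.05, 90% power.

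n = [(1.960·√(0.01·0.99) + 1.282·√(0.03·0.97)) / 0.02]² = 427.7, so 428 in Arm 2. Then 428 × 7/6 = 499.3, taken as 500 (72 + 428), and 500 × 1.05 = 525. The figures reproduce. At 1:6, 525 randomised gives 525/7 = 75 in Arm 1 and 450 in Arm 2. The plan states no size for the safety population.

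**Dilution.** Let N be the number randomised to Arm 1, k the number never treated and r the related-event rate among the treated. Expected events are r(N − k), so the rate by the written definition is r × (N − k)/N. Arm 2 is not diluted. With equal true rates, the apparent Arm 2/Arm 1 ratio is N/(N − k). The values of k and the 10% rate are assumptions; neither is in the documents.

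| Never treated, of 75 | Share | Factor | A true 10% appears as | Apparent ratio, Arm 2/Arm 1 |
|---|---|---|---|---|
| 0 | 0% | 1.000 | 10.0% | 1.00 |
| 2 | 2.7% | 0.973 | 9.7% | 1.03 |
| 4 | 5.3% | 0.947 | 9.5% | 1.06 |
| 8 | 10.7% | 0.893 | 8.9% | 1.12 |

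With N = 72, 4 or 7 never treated gives 68/72 = 0.944 or 65/72 = 0.903. If replacement tops Arm 1 up to 75 treated while the replaced patients stay in the set, 4 or 8 such patients give 75/79 = 0.949 or 75/83 = 0.904. The factor does not depend on r. Requiring receipt of product in both arms returns it to 1.

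**In percentage points.** The shift is r × k/N. For k = 4 to 8 of 75 it is 0.1 to 0.2 points if r is 2%, and 0.5 to 1.1 points if r is 10%. For scale, the standard error of a 10% rate in 75 patients is √(0.10 × 0.90/75) = 3.5 points.

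**Wrong product.** One Arm 1 patient given PD G 506 A who has a related event adds 1/75 = 1.3 points to Arm 1 (1/72 = 1.4). Grouped by product received, she would add about 1/450 = 0.2 points to the drug group.

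**Part A.** About 75 patients receive PD G 506 A in Part A. If everyone in Arm 2 is dosed, they make up 75/(75 + 450) = 14% of exposed patients, or 75/(75 + 428) = 15%.

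**The case against.** The best case against is that little hangs on this. The safety summary is descriptive, no test or decision depends on it, and the dilution is small beside sampling error in an arm of 72 to 75. For drug-related events the placebo rate should be near zero, so there is little to dilute. Section 7.4 writes the safety endpoints as counts without a denominator, so the effect arises only if the safety population supplies one. All of that stands and limits the size. It does not explain why the two arms should have different entry rules.

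Several stronger readings are tempting and are not supported:

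- *Never-treated Arm 1 patients have no events at all.* Section 13.3 records events from consent, so they can contribute adverse events until withdrawal. The zero holds only for treatment-related events.
- *The plan's 5% is the never-dosed share.* Section 15.2 calls it loss to follow-up. A 10% share has no source either.
- *The gap is one to two percentage points.* With 5 to 10% undosed that needs an event rate near 20%, and the documents give no event rate.
- *Thirty days usually pass between randomisation and surgery.* Enrolment needs all eligibility criteria met, including laboratory limits, and the blood work must fall within 7 days before dosing. In practice the interval is probably shorter.
- *A mis-dosed Arm 1 patient will be counted as placebo.* Section 15.4.2 does not say as randomised. The inference rests on entry by randomisation, summary by arm and no as-treated rule. Such an event would not be hidden: Section 13.4.1.3.1 requires medication errors to be reported on serious-event timelines, and Section 13.4.1.1 requires causality to be assessed for each event.

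Sections 15.1 and 15.8 defer detail to the SAP. The text reviewed contains only the protocol's statistical section, so a later SAP may add a grouping rule. It cannot be assumed to override the protocol's definition.

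**Conclusion.** The asymmetry is explicit and should be corrected. Following the definition as written multiplies the Arm 1 related-event rate by treated/randomised: 1.00 if nobody is lost before dosing, about 0.90 if one in ten is. This rests on an assumed never-treated share of 0 to 10% and on the safety population being the denominator.

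A reader might infer that the rule hides drug harm. The dilution does the reverse, since it makes Arm 2 look relatively worse. The wrong-product gap would favour the drug, but it is an inference, no frequency for it is documented, and the two cannot be relied on to cancel. The exclusion of Part A is a plain conflict between Section 15.4.2 and Sections 8.1 and 15.2. None of this touches the primary efficacy analysis.

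**What to change.** Rewrite Section 15.4.2, and carry the same text into the SAP, so that the safety population is: all Part A patients who receive PD G 506 A, and all Part B randomised patients who receive any amount of study product (PD G 506 A or placebo), grouped by the product actually received. Show Part A and Part B separately and together, as Section 15.2 already provides.

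The cost is one sentence and a slightly smaller Arm 1 denominator; with 0, 2, 4 or 8 of 75 never treated it becomes 75, 73, 71 or 67.

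One related imbalance remains. Under Section 11.1, safety data continue after withdrawal only for patients who received PD G 506 A, so a placebo patient who withdraws after dosing loses safety follow-up. The new definition does not cure that, and the safety report should state it.
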